## APPLICATION & PROTOCOL

breakfast if the study team determines it is necessary.

### Summary of samples collected for Brussels Sprouts and DIM cycles

Time point	Total blood collected (mL)	Urine
-7 days	25	Spot
0 (background)	25	Spot
0.25 – 24 hours	90 (9 x 10 mL)	Total urine (0-48 hours)
48 hours	15	

The total amount of blood collected for the BaP-only cycle is 120 mL. The total amount of blood collected for the Brussels sprouts and DIM cycles is 155 mL per cycle.

Subjects who indicate that they have not consumed the Brussels sprouts or DIM capsules as instructed will be allowed to have up to two lapses with subsequent washout and dietary restriction extension before they will be automatically removed from study participation due to lack of compliance.

There will be at least three weeks' washout period between cycles. Previous multiple micro-dosing of the same individual has shown that after 3 weeks there is no detectable [C] in plasma or urine, validating the choice of 3 weeks as adequate for a "washout period". Extending the washout period will not adversely impact the data collected from the subjects but will minimize the subject's exposure to PAHs.

Subjects who have participated in IRB protocol 8233 (Benzo[a]pyrene Ultralow Dose-Response Study) or IRB protocol 8554 (Ultralow Dose PAH Binary Mixture Study) will participate in only the [C]-BaP plus DIM and [C]-BaP plus Brussels sprout cycles if they have complete the 50 ng [C]-BaP-only cycle within the prior 12 months. There is no set order to the Brussels sprouts or DIM cycles.

Subjects will be asked to defer blood donation for one month before, throughout, and for one month after completion of the study. At any point during the study, subjects will be referred to their physician if the study physician or nurse consider this advisable.

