Our hypothesis is that pre-administration of Brussels sprouts or 3,3'-diindolylmethane (DIM) will alter [C]-BaP metabolism and increase the rate of elimination consistent with predictions based on a previously developed Physiologically-Based Pharmacokinetic (PBPK) model for BaP. Briefly, this hypothesis will be tested by dosing individuals with 50 ng [C]-BaP alone and, following a 3-week washout period, ingestion of ½ cup (about 44 g) Brussels sprouts or 300 mg of 3,3'-diindolylmethane (DIM) supplement for 1 week prior to the [C]-BaP micro-dose. The impact of the supplement and the whole food will be assessed with respect to alterations in uptake from the GI tract, metabolism and rate of elimination. To date, our accelerator mass spectrometry (AMS) studies with PAHs have not investigated the impact of diet on [C]-BaP pharmacokinetics. The consumption of cruciferous vegetables will be assessed at the beginning of the study by completion of a dietary questionnaire to examine typical eating patterns in the previous 3 months and by collection and extraction of blood and urine to assay for DIM by LC/ESI-MS/MS-SRM. In addition, for each phase, urine will be assayed for DIM as an estimate of crucifer or DIM supplement intake. [C]-BaP and metabolites will be extracted from plasma and urine (with and without  $\beta$ -glucuronidase/sulfatase) and shipped to Lawrence Livermore National Laboratory (LLNL) for UPLC-AMS analysis. The PK parameters will be assessed at PNNL and the impact of Brussels sprout or DIM consumption on uptake, metabolism and elimination of [C]-BaP determined. In preclinical and clinical studies administration of Brussels sprouts or DIM impacts the activity of the same enzymes responsible for the phase 1 (CYP1A1 and CYP1B1) and phase 2 enzymes (GSTM1, UGT, SULT). Monitoring changes in  $\beta$ -estradiol metabolites will confirm the mechanism of alteration in the metabolic profile of [C]-BaP.

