### Cycle 1: [C]-BaP capsule only

The IV catheter will be placed in an appropriate vein in the forearm or antecubital region by the nurse coordinator. Subjects will swallow a capsule containing the [C]-BaP with 100 mL water. Prior to micro-dosing with [C]-BaP, a time zero blood sample of 20 mL will be collected with 10 mL analyzed for background plasma levels of BaP (and 62 additional PAHs) with GC-MS/MS and the remaining 10 mL analyzed for [C]-BaP and metabolites as with subsequent time points.

Blood will be sampled at 0, 0.25 0.5, 1.0, 1.5, 2, 3, 4, 8, 24, and 48 hours (11 draws total, 8-9 of which come from the catheter). The catheter will remain in place for blood draws through hour 4. After the 4 hour blood draw, subjects will have the choice of having the catheter removed and returning for the 8 hour blood draw by straight stick, or they can keep the catheter in place and remain on-site until after the 8 hour blood draw. The subjects will be monitored by the nurse coordinator between blood draws. The 8 (possibly), 24, and 48 hour blood draws will be done with straight stick phlebotomy. No more than three (3) skin punctures will be made in an attempt to draw blood at each visit. The first blood draw of this cycle will be 20 mL and then subsequent blood draws will be 10 mL.

Subjects will be instructed to collect all urine during the entire 48-hour study cycle in containers provided by the study team.

Two hours after swallowing the capsule, a standardized breakfast will be provided, after which subjects may resume normal eating and drinking. Snacks or fluids will be provided prior to the standardized breakfast if the study team determines it is necessary.

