## APPLICATION & PROTOCOL

### **Cycles 2 and 3: [C]-BaP capsule with Brussels sprouts and [C]-BaP capsule with DIM**

Visit 0 (20 minutes): Seven days before the capsule is taken, subjects will come to the CRC for a spot urine collection (analyzed for DIM and β-estradiol metabolites) and 25 ml blood sample (analyzed for background BaP and 62 other PAHs, DIM, β-estradiol and metabolites.) They will pick up their study Brussels sprouts or DIM capsules as described below:

*Brussels sprouts:* Subjects will be provided 7 days' servings of frozen, pre-cooked Brussels sprouts. Each serving will be about 50 grams (about ½ cup) of frozen Brussels sprouts. Study team members will record serving weights before providing to subjects and serving weights will be standardized as much as possible. Subjects will be instructed to consume one serving with dinner (defrost, warm and season, if desired) during the 7 days prior to the study cycle.

*DIM capsules:* Subjects will be provided 7 days' worth of BioResponse DIM® 150 capsules. They will be instructed to take 2 capsules (300 mg total) each evening with dinner during the 7 days prior to the study cycle.

The IV catheter will be placed in an appropriate vein in the forearm or antecubital region by the nurse coordinator. Prior to micro-dosing with [C]-BaP, a time zero blood sample of 25 mL will be collected with 10 mL analyzed for background plasma levels of BaP (and 62 additional PAHs) with GC-MS/MS and the remaining 15 mL analyzed for DIM as well as β-estradiol and metabolites. Fifteen mL will be taken at the 48 hour time point to determine what changes may have occurred in blood and urine levels of DIM and estrogens. Subjects will swallow a capsule containing the [C]-BaP with 100 mL water. For the DIM study cycle, subjects will also take 2 capsules (300 mg BioResponse DIM®) with the [C]-BaP capsule.

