## APPLICATION & PROTOCOL

	BioResponse DIM® 150 (purchased locally) will be used as the standardized source of 3,3'-diindolylmethane (DIM). We have chosen the BioResponse supplement, rather than purchasing and encapsulating DIM from a chemical supply company, as the oral bioavailability is significantly greater  and it more accurately reflects human consumption.			
9	Method/route of administration:			
	Subjects will be instructed to take 300 mg (2 x 150 mg capsules) orally with dinner for 7 days prior to the study cycle.			
10	Mechanism of action:			
	In animal models, DIM is capable of inducing or inhibiting phase 1 (e.g., CYP1A1; CYP1B1) and phase 2 (e.g., GSTM1 or UGT1A10) enzymes known to metabolize BaP for elimination. In human clinical trials (for prevention of breast cancer) it has been shown to increase the ratio of (2-hydroxy E2/16 $\alpha$ -hydroxy E2). The 2-hydroxy metabolite is sometimes referred to as the “good estrogen” and 16 $\alpha$ -hydroxy as the “bad estrogen”  . CYP1B1 is capable of metabolizing estrogen to 4-hydroxy-estrogen which is a “catechol” capable of producing oxidative stress at high levels. DIM actually does not impact CYP1B1 markedly and most reports from animal studies indicate inhibition (which would be protective).			
11	Known drug interactions:			
	It is possible that DIM could impact the metabolism of other substrates for these enzymes. However, CYP1A1 and CYP1B1 (required for formation of carcinogenic metabolites) rarely are involved in metabolism of drugs. This fact and our exclusion criteria with respect to use of therapeutic drugs makes drug interaction unlikely. There are no known drug interactions in humans taking DIM reported in the literature. In addition, the impact of DIM would be transient as it has a half-life in humans of a few hours. Any induction or inhibition of enzymes would only last 1-3 days as these enzymes turnover fairly rapidly. It is possible that there could be a transient change in estrogen metabolite levels in women taking DIM.			
12	Manufacturer/Sponsor:			
	BioResponse, LLC			
13	Manufacturer/Sponsor Location:			
	Boulder, Colorado			
14	Name of supplier:			

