## APPLICATION & PROTOCOL

7	For each radioactive material , indicate the activity (mCi) per single dosage, and the total number of dosages per single study and per complete research protocol. A single study is comprised of all dosages received by the participant during a single visit/session.				
7a	Radioactive material name:				
	[7-  C]-benzo[a]pyrene (BaP), specific activity 27 µCi/µmol				
7b	mCi dosage:				
	0.0000054				
7c	Total dose per participant, per study visit:				
	1				
7d	Total exposure per participant, per protocol:				
	3 (or 2- if subject has completed Protocol 8233 or Protocol 8554 within the past 12 months, they will complete only the Brussels sprouts and [  C]-BaP cycle and DIM and [  C]-BaP cycle, not [  C]-BaP -only cycle)				
8	Radioactive drug(s) prepared on-site will be prepared, assayed, tested, and labeled in accordance with the FDA's requirements?				
9	Radioactive drug(s) prepared on-site will be prepared, assayed, tested, and labeled in accordance with an Radioactive Drug Research Committee's ( RDRC ) requirements?				
SECTION 29 - Biological Samples			Yes	No	N/A
1	Does the study involve the collection or receipt of biological samples?			Skip to section 30	
1a	If yes, indicate what biological samples will be received or collected:				
	Blood and urine				
2	Will samples be obtained prospectively from living individuals?				
3	Where possible, risks should be minimized by using procedures already being performed on the subjects for diagnostic or treatment purposes. Check all that apply:				

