## APPLICATION & PROTOCOL

**PI should email completed application and all relevant attachments to [contact]**

## Statistical Analysis Plan

Pharmacokinetic parameters were evaluated for linearity using a best fit modeling approach. First, pharmacokinetic parameters were evaluated for significant change as a function of dose using a standard linear regression model including a fit y-intercept. Slopes were compared using a *t*-test and an alpha value of 0.05. If the parameter changed as a function of dose, we further evaluated the parameter with a linear regression model, with *k* as the slope through the origin and a Michaelis-Menten model, which assumes saturation at  $V_{max}$  and an affinity constant *K*, to individual parameters (*p*) as a function of external [ $^{14}\text{C}$ ]-BaP dose. The Bayesian information criterion (BIC) was used to judge the best-fit model and provide evidence of linear or saturable pharmacokinetics.

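### The sprouts/DIM order is not assigned, and because BaP-alone always comes first, a step after that cycle cannot be told from a diet effect

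*Combined protocol and SAP*

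**What the plan says.** Section 20 labels the cycles "Cycle 1: [ 14 C]-BaP capsule only" and "Cycles 2 and 3: [ 14 C]-BaP capsule with Brussels sprouts and [ 14 C]-BaP capsule with DIM". Section 13 item 1 describes the same sequence: BaP "alone and, following a 3-week washout period, ingestion of" sprouts or DIM. On the order of the two diet cycles, Section 20 says only "There is no set order to the Brussels sprouts or DIM cycles". The documents describe no randomisation, counterbalancing or sequence list.

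Participants from protocols 8233 or 8554 omit Cycle 1 if they completed the 50 ng "BaP-only cycle within the prior 12 months". By implication that earlier cycle is their reference, so BaP-alone still comes first. Section 28 item 7d words the rule differently: "if subject has completed Protocol 8233 or Protocol 8554 within the past 12 months, they will complete only the Brussels sprouts". One version counts the 12 months from the 50 ng cycle, the other from completing the earlier protocol.

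Section 20 sets a three-week minimum between cycles and no maximum. Section 19 sets the same minimum between BaP doses given in this study and in the earlier ones.

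The SAP states that "pharmacokinetic parameters were evaluated for significant change as a function of dose using a standard linear regression model". This protocol gives a single BaP dose of 50 ng (Section 24 item 7). The SAP contains no comparison between conditions and no term for condition, cycle or sequence.

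**The concern.** The hypothesis in Section 13 is that each diet intervention changes BaP metabolism and elimination compared with BaP alone. In every participant the BaP-alone dose is the earliest of the three. Anything that shifts the measurements between that dose and both later ones therefore enters both main contrasts as if it were a diet effect.

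The comparison of sprouts with DIM could be protected by balancing their order, but nothing in the plan does so. The split of orders among about 7 completers is left to scheduling or habit, and a lopsided split lets a later-cycle effect pass for a difference between the whole food and the supplement.

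For roll-over participants the reference also comes from another protocol and may be months old.

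**Working it through.** The plan gives no calculation to reproduce. The inputs are 7 completers (Section 14), BaP-alone first, and the diet cycles second and third (Section 20). Let n1 participants take sprouts first and n2 = 7 − n1 take DIM first. S and D are the log-scale effects of sprouts and DIM against BaP-alone. Drift sizes are assumptions.

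**Step s after the BaP-alone cycle.** Every participant's sprouts difference from BaP-alone estimates S + s, and every DIM difference estimates D + s. Only these sums are determined. A model with participant, condition and step has rank 9 of 10 at 4:3, 5:2, 6:1 and 7:0. Neither main contrast is estimable and each carries a bias of exactly s. In DIM − sprouts the step cancels.

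**Drift d per cycle, DIM vs sprouts, unadjusted.** Sprouts-first participants contribute +d and DIM-first participants −d, so the bias is d(n1 − n2)/7. Only the diet cycles enter, so this also covers roll-overs. The last two columns show the ratio when there is no true difference.

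| Split | Bias | 5% per cycle | 10% per cycle |
|---|---|---|---|
| 4:3 | d/7 | 1.007 | 1.014 |
| 5:2 | 3d/7 | 1.021 | 1.042 |
| 6:1 | 5d/7 | 1.035 | 1.070 |
| 7:0 | d | 1.050 | 1.100 |

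For example, at 6:1 with 10%: 1.10^(5/7) = 1.070. These drift sizes are illustrations only.

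**Can a linear drift be adjusted for?**
- *Per cycle, one order.* The data give S + d and D + 2d: two equations in three unknowns. Rank is 9 of 10 and no contrast is estimable.
- *Per cycle, both orders.* The second order adds D + d and S + 2d, so d can be estimated (rank 10 of 10), imprecisely. At 4:3 the variances of sprouts and DIM vs BaP-alone are 0.88 and 1.01 times the within-participant variance, against 2/7 = 0.286 without the term.
- *In calendar time, one order.* With equal gaps (doses at weeks 0, 3 and 6 for all), rank is 9 of 10. With assumed unequal gaps (four participants at weeks 0, 3, 6; three with references 20, 30 and 40 weeks before the first diet dose and 3 weeks between diet doses), rank is 10 of 10 and the variances are 0.505 and 0.605. The drift is then estimable, but only through gaps that nobody controls.

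**Cost of a period term in sprouts vs DIM.** In units of the SD of the paired difference, the adjusted 95% half-width is t(0.975, 5) × √[(1/n1 + 1/n2)/4], and the unadjusted one is t(0.975, 6)/√7 = 0.925.
- 4:3: 0.982/0.925 = 1.06
- 5:2: 1.075/0.925 = 1.16
- 6:1: 1.388/0.925 = 1.50

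**Blocks of 2 and 7 completers**, assuming drop-out is unrelated to order. If 8 start, the split is always 4:3. If 10 start, 5:2 has probability 2 × C(5,5) × C(5,2)/C(10,7) = 20/120 = 17%. If 12 start, 5:2 has 180/792 = 23% and 6:1 has 12/792 = 1.5%.

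**Age of the roll-over reference.** It is at least 3 weeks at the first diet dose and at least 3 + 3 = 6 weeks at the second. The 12-month limit has no stated end point and cycle gaps have no maximum, so the age may be about 12 months or more.

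**The case against.** The best case for the plan is that BaP-alone belongs first. A reference taken before any sprouts or DIM cannot carry over their effects. For DIM, Section 25 item 11 says "Any induction or inhibition of enzymes would only last 1-3 days as these enzymes turnover fairly rapidly"; no figure is given for sprouts. This stands, and moving the cycle is not proposed.

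The documents also name no source of drift, and several controls limit one: undetectable label after three weeks, diet restriction, fasting, a standardised breakfast, quarterly stock checks and capsule quality control. This makes a large drift less likely. The washout evidence concerns residual label rather than other differences between cycles, and the aliasing of a step does not depend on its size.

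Both orders may well occur by chance. If each participant independently took either order with probability 0.5, both would appear among 7 with probability 1 − 2(0.5)^7 = 98.4%; if one order were used 90% of the time, 52.2%. The documents give no such probability, and both orders occurring is not the same as balance.

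The study says it is not powered to generalise, and the hypothesis states no head-to-head test of sprouts against DIM. That keeps the point modest.

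A reader might infer that a linear drift can be separated only if both orders occur. The documents do not support that in general: it holds for drift counted per cycle or with equal gaps, and the plan fixes only a minimum gap. A reader might also put the roll-over reference at 3 weeks to 12 months old. That range fits at most the first diet cycle.

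**Conclusion.** The point holds as a low-cost improvement, not as a flaw that invalidates the study. The comparisons with BaP-alone are before-after comparisons, and a step after the BaP-alone cycle is inseparable from diet at every split of orders. Sprouts vs DIM carries an avoidable order bias of d/7 to d, depending on how the unassigned orders fall.

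These results assume 7 completers and a log-scale model with additive participant and condition effects. The size of d or s is unknown. The documents do not show that any drift exists, and randomising the diet order would not cure the step.

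**What to change.** In Section 20, replace the sentence on order with:

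*The order of the Brussels sprouts and DIM cycles will be randomised for each participant who starts the first diet cycle, in permuted blocks of 2, and recorded.*

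Add to the SAP:

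*PK parameters will be compared between conditions within participant on the log scale. Sprouts vs DIM will include a period term (first vs second diet cycle). Sprouts vs BaP-alone and DIM vs BaP-alone will be reported as before-after comparisons, with days from the reference BaP-only dose to each diet-cycle dose listed per participant, and a sensitivity analysis excluding participants whose BaP-only cycle came from 8233 or 8554.*

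Do not add a linear cycle term: a roll-over's reference dose has no cycle number in this protocol. If a drift check is wanted, use days since the reference dose as the time variable, label it exploratory, and state that it does not address a step. Reconcile the 12-month wording in Section 20 and Section 28 item 7d.

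The cost is a short randomisation list, supplies issued in the assigned order, more cautious wording of the main contrasts, and a sprouts-vs-DIM 95% CI wider by about 6% at 4:3, 16% at 5:2 or 50% at 6:1. The sensitivity analysis checks the effect of using an earlier-protocol reference only, and it will be weak: relative to 7 participants, its CI is about 1.7 times as wide with 4 left and 2.7 times with 3.

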#### Processing of samples:

Blood samples will be centrifuged to obtain plasma and peripheral blood mononuclear cells (PBMCs). The [C]-BaP and metabolites will be extracted directly from plasma by liquid/liquid extraction with ethyl acetate. The urine will be pooled over the time periods pre-capsule (baseline), 0 – 12, 12-24, and 24-48

## APPLICATION & PROTOCOL

hours. After volumetric quantitation of each pool of urine, 12 mL will be collected, 4 mL will be adjusted to pH 5 and half treated with  $\beta$ -glucuronidase/sulfatase prior to extraction with ethyl acetate. The plasma and urine extracts will be blown down under argon, sealed in amber vials and shipped to LLNL where they will be injected onto an Ultra-Pressure Liquid Chromatograph (UPLC) interfaced via a “moving wire” into the AMS. We will be able to determine femto ( $10^{-15}$ ) g/mL levels of BaP and BaP metabolites (by co-elution with unlabeled standards available from the OSU Superfund Research Center PAH repository). The time-course of blood and urine levels of parent BaP and metabolites will be used to construct a pharmacokinetic model. In addition, DNA isolated from PBMCs at 0 hr and 48 hr will be counted directly on the AMS to check for levels of covalent DNA binding.

DIM levels in blood and urine will be measured as follows: Triplicate samples from each time point or pooled urine samples will be spiked with [ $^2\text{H}_2$ ]DIM internal standard and incubated 20 hours at 37°C with  $\beta$ -glucuronidase/arylsulfatase. Samples will then be extracted twice with t-butyl methyl ether, solvent evaporated with nitrogen stream, and DIM levels determined. We will utilize the recently developed LC/ESI-MS/MS-SRM assay from [name] (a collaborator on the NIH grant funding this work) group as a biomarker of both DIM and Brussels sprouts consumption.

The levels of  $\beta$ -estradiol and metabolites (2-, 4- and 16 $\alpha$ -hydroxylated, conjugated and total) is assessed by a UPLC-tandem mass spectrometry method. Briefly, 2 mL of serum is divided into equal fractions with 1 treated with glucuronidase/arylsulfatase for deconjugation. A liquid-liquid extraction with MTBE is performed and the estrogens derivatized with pyridine-3-sulfonyl chloride, re-extracted with MTBE, evaporated to dryness under nitrogen and then taken up in 20% methanol in water prior to injection onto a UPLC column interfaced to a TSQ mass spectrometer by electro-spray ionization. The identity of each metabolite will be determined by UPLC retention time and SRM-MS. [name] [name], Director of the Linus Pauling Institute, has expertise with this assay and is available for consultation if needed.

